Important note (1)	
A new escalation will be performed after 4 weeks of observation of at least three patients at the previous level if no dose-limiting toxicity (DLT) is observed.
 
If there is DLT at a dose level (clinically relevant, grade 3 or 4 toxicity or inability to complete 50% of treatment administration due to AEs) in the first four weeks, three new patients will be included at the same level. If a second patient has dose limiting toxicity at that dose level, the dose level will be declared above the MTD and the next lower dose level will be expanded to six patients from three patients. The next lower dose level will be declared the MTD providing that no more than 1 patient of six has dose limiting toxicity (or < one third of patients have DLTs). Once the presumed MTD is found, this dose will be set as the RP2D and the first part of the phase 2 study begins. Bayesian toxicity monitoring will be performed throughout the phase 2 study to ensure that the DLT for the tri-therapy is no more than 33% with high confidence. If greater than or equal to one third of patients have DLT, then next lower dose is MTD and that dose will be expanded in the same way.

Important note (2)	
The Clinical Monitoring Committee (CMC) constituted by all principal investigators will meet at least monthly by teleconference to discuss the patients included in the study, with the purpose of monitoring and managing any toxicity related issue.

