Important note (3)	
A key point will be to understand the contribution of each of the drugs in generating toxicities. To this purpose, the CMC will specifically investigate whether observed toxicities relate to overlapping effects (such as fatigue, nausea diarrhea) or specific toxicities (such as febrile neutropenia – palbociclib) or low platelets level (axitinib). Appendix 8 describes all observed toxicities and outlines common or specific toxicities. Main toxicities specific to each drug are summarized in Important note (5).
 
Rules in case of toxicity/dose modifications:
 
For any Grade 3 dose-limiting toxicity (see page 32 for dose-limiting toxicity definitions) that is deemed to be drug specific, that drug will be held until resolution to <Grade 1. The drug will then be restarted with the dose at the next lowest level. If Grade 3 or greater toxicity recurs, the drug will be permanently stopped. Exception is hematologic toxicity which may be handled as in Important note (5), palbociclib section or Important note (6).
 
If a toxicity has been deemed to be due to a single drug, but persists at <math>\geq</math> grade 3 level after stopping the drug, all drugs will be stopped.
 
If it is unclear as to the drug that is causing a toxicity, all three drugs will be held.

	
Toxicities that may be clearly attributable to avelumab include immune toxicities such as immune mediated pneumonitis, hepatitis, colitis and nephritis, and infusion related reactions.
 
Toxicities clearly attributable to axitinib include hypertension and proteinuria.
 
Toxicities clearly attributable to palbociclib include lowering of white blood cells (WBC) or platelet counts.
 
For Grade 4 dose limiting toxicities, the drug to which it is attributable will be permanently stopped. If it is not clear as to which drug is associated with the toxicity, all drugs will be permanently stopped.
 
A Clinical Monitoring Committee (that includes site PIs) may be convened to help decide to which drug the toxicity is attributable.

Important note (4)	For dose interruption and reduction events, accurate medical administration records will be maintained to capture changes in dosing regimens, including concomitant medications.

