### Toxicity management

The most common ( $\geq 2\%$ ) Grade  $\geq 3$  adverse reactions of palbociclib were neutropenia, leukopenia, anaemia, fatigue, and infections

1. Monitor complete blood counts prior to starting palbociclib therapy and at the beginning of each cycle, as well as on Day 14 of the first 2 cycles, and as clinically indicated
2. Dose interruption, dose reduction or delay in starting treatment cycles is recommended for patients who develop Grade 3 or 4 neutropenia
3. Special warning is febrile neutropenia has been reported in about 1% of patients exposed to palbociclib.
4. Guidelines for dose adjustments for hematologic toxicities attributable to palbociclib
  - Grade 3: No dose adjustment is required. Consider repeating complete blood count monitoring one week later. Withhold initiation of next cycle until recovery to Grade  $\leq 2$ .
  - Grade 3 ANC ( $<1000$  to  $500 \text{ mm}^3$ ) + Fever  $\geq 38.5^\circ\text{C}$  and/or infection: Withhold palbociclib and initiation of next cycle until recovery to Grade  $\leq 2$  ( $\geq 1000/\text{mm}^3$ ). Resume at next lower dose.
  - Grade 4: Withhold palbociclib and initiation of next cycle until recovery to Grade  $\leq 2$ . Resume at next lower dose

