**Recurrent Grade 3 ADRs and Grade 3 infusion-related reaction require permanent discontinuation.**

**Any Grade 2 ADR should be managed as follows:**

- If a Grade 2 ADR resolves to Grade  $\leq$  1 by the last day of the current cycle, treatment may continue.
- If a Grade 2 ADR does not resolve to Grade  $\leq$  1 by the last day of the current cycle, infusions should not be given on the following cycle. If at the end of the following cycle the event has not resolved to Grade 1, it should be treated as a Grade 3 or 4 (except for hormone insufficiencies, that can be managed by replacement therapy; for these hormone insufficiencies, up to 2 subsequent doses may be omitted).
- Upon the second occurrence of the same Grade 2 ADR (except for hormone insufficiencies that can be managed by replacement therapy) in the same subject, treatment with avelumab has to be permanently discontinued.

Important note (6):	Specific protocol dose modification for toxicity management related to palbociclib: 

- In case of recurrent grade 3 hematologic toxicities, palbociclib may be reduced to 75 mg po daily one week off and one week on.

- In case of other severe (<math>\geq</math> grade 3) toxicity related to palbociclib, consider holding palbociclib until toxicity is grade 1 or less, then resume at the alternate schedule of 2 weeks OFF / 2 weeks ON.

----------------------------	---

- **DLT will be defined as:**

Any of the following events that are considered to be clinically significant and meaningful as per evaluation of the attending physicians and confirmed by CMC and at least possibly related to drug. DLTs for the purposes of dose-escalation will be evaluated during the 28-day period following the first dose of study treatment. Each treatment cycle is four weeks. Toxicities will be graded and documented according the NCI CTCAE (v4.03).

- **Non-hematological dose-limiting toxicity is defined as:**

- Persistent Grade 3 or 4 hypertension despite treatment with anti-hypertensive drugs.
- Grade 3 or 4 Gastrointestinal bleeding.
- Grade 3 or 4 Gastrointestinal perforation or fistula.
- Development of Reversible Posterior Leukoencephalopathy Syndrome.
- Persistent Grade 3 or 4 proteinuria.
- Grade 3 or 4 arterial or venous thromboembolic events.

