- Any other Grade 3 or Grade 4 non-hematological toxicity that are considered at least possibly related to a study drug and clinically significant after discussion at CMC with exceptions listed below:  
grade 3 nausea, vomiting, diarrhea, that responds to maximal supportive treatment(s) within 3 days, grade 3 liver enzyme elevation, including ALT/AST/GGT that returns to Grade  $\leq 1$  or baseline prior to the time for the next treatment cycle.
- Allergic reactions that necessitate discontinuation of the study drug responsible for the reaction.
- Any Grade  $\geq 2$  pneumonitis of any duration.

- **Hematological dose-limiting toxicity is defined as:**

- Grade 4 neutropenia (absolute neutrophil count, ANC) for  $> 7$  days
- Platelet count  $< 10,000/\text{mm}^3$  one time or bleeding requiring transfusion
- Toxicity that causes a delay of  $> 14$  days between treatment cycles
- Febrile neutropenia despite G-CSF secondary prophylaxis
- Either isolated or recurrent (i.e., cardiac, renal, neurologic) toxicity that is judged by the Investigator to be a DLT.

- **Further evaluation of the combination's toxicity at a dose level:**

Up to 3 additional patients could be added at a dose level to explore the toxicity on an occasional basis after discussion with the CMC. All additional patients will be included in the study's assessment.

- **To decide for dose-escalation cohort at a higher dose level,** the CMC that includes the study investigators and the sponsor clinical study team, will review available data (e.g. safety profile). Subsequent safety reviews by the CMC will be conducted prior to enrollment of patients in a new cohort and to establish the RP2D.

- **Intra-patient dose escalation:**

Patients will be permitted to have a dose escalation to the highest dose shown to be safe at the time of escalation, provided they have no clinically relevant drug-related toxicity  $>$  Grade 1 at the dose

level they are on and that both they and their physician deem a dose escalation to be in their interest. For a dose level to be considered proven safe, there must be at least three patients treated at that dose level for at least four weeks, and the clinical monitoring committee must have deemed that dose level to be at or below the MTD.

- **Dose reduction**

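### The DLT item for a cycle delay of more than 14 days cannot be met within the 28-day escalation window, and no rule counts or waits for it

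*Combined protocol and SAP*

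**What the plan says.** All places are in section 3.3.1 unless noted.

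- **DLT list.** Important note (3) points to the list for DLT definitions ("see page 32 for dose-limiting toxicity definitions"). One hematological item is "Toxicity that causes a delay of" more than 14 days between treatment cycles. The last item admits "toxicity that is judged by the Investigator to be a DLT".
- **Window.** The paragraph introducing the list says: "DLTs for the purposes of dose-escalation will be evaluated during the 28-day period following the first dose of study treatment". It sets the cycle at four weeks and requires the Clinical Monitoring Committee (CMC) to confirm DLTs.
- **Escalation rule, Important note (1).** "A new escalation will be performed after 4 weeks of observation of at least three patients at the previous level", if no DLT is seen. It counts DLTs in the first four weeks, with its own short description: "clinically relevant, grade 3 or 4 toxicity or inability to complete 50% of treatment administration due to AEs". A lower level is accepted as the MTD "providing that no more than 1 patient of six has dose limiting toxicity", also expressed as fewer than one third of patients.
- **Palbociclib management, Important note (5).** For grade 3 hematologic toxicity: "No dose adjustment is required. Consider repeating complete blood count monitoring one week later. Withhold initiation of next cycle until recovery to Grade" 2 or lower.
- **CMC review.** The CMC reviews available data before each new cohort and before the RP2D is set.
- **Section 7.1** describes DLT as grade 3 non-hematological or grade 4 hematological toxicity. **Section 7.3** gives phase 2 toxicity boundaries, the first being 4 of 10 patients.

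**The concern.** A between-cycle delay can only start accruing once cycle 2 is due, which is after the 28-day window has closed. No text assigns a late cycle 2 to cycle 1, lengthens the window for it, or holds a decision while a delay is running. The CMC could therefore open the next level, clear the current level for intra-patient escalation, or set the RP2D while a treated patient has a toxicity that later meets a listed DLT criterion.

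The item matters more with this regimen than with many. Palbociclib is taken on days 8 to 28 (Appendix 5), so exposure runs to the last day of the window and recovery from a full course falls after it. From dose level 2 to 4, only palbociclib rises (75, 100, 125 mg), and neutropenia and leukopenia are among its most common reactions of grade 3 or higher. For grade 3 hematologic toxicity the protocol asks for no dose change but withholds the next cycle, so the delay may be the main objective marker of such an event.

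**Working it through.** **Inputs.** Window 28 days and cycle four weeks (section 3.3.1, DLT definition; Appendix 5, footnote 12). Delay threshold more than 14 days (DLT list). Avelumab dosing window of -1/+3 days on day 1 of each cycle (Appendix 5, footnote 6). Decision rule in Important note (1).

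**Stated window.** 4 × 7 = 28 days, which agrees with the 28-day window and the 28-day cycle.

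**First day on which the item can be met** (scheduled start of cycle 2 + 15 days, the first day that is more than 14 days late):

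| Reading | Cycle 2 due | First met | Days after day 28 |
|---|---|---|---|
| Nominal | 28 + 1 = 29 | 29 + 15 = 44 | 16 |
| Dosing window, -1 day | 28 | 43 | 15 |
| Dosing window, +3 days | 32 | 47 | 19 |

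Counting the gap from the last oral dose on day 28 gives 28 + 15 = day 43. The loosest reading, a gap of more than 14 days after the day 15 avelumab dose, gives 15 + 15 = day 30. Every reading falls after day 28.

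**Staggered entry.** At the earliest decision, when the last starter reaches day 28, a patient who started s days before is on day 28 + s. The item is settled on nominal days only if 28 + s ≥ 44, that is s ≥ 16. Patients with s from 0 to 15 are still open, and the last starter always is. As an assumption, take even accrual of about 30 phase 1 patients over 6 to 8 months of 30.4 days. That gives one patient every 6 × 30.4 / 30 = 6.1 to 8 × 30.4 / 30 = 8.1 days. The first of three then leads the third by 12.2 to 16.2 days and is at about day 40 to 44. At that pace at least two of the three, and often all three, are unsettled on the earliest decision day.

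**Effect of one uncounted event under Important note (1).**

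- 0/3 = 0%: escalate. 1/3 = 33.3%: add three patients.
- 1/6 = 16.7%, below one third: accepted as MTD. 2/6 = 33.3%, not below one third: not accepted.

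**What the other routes leave open.** Section 7.1 covers grade 4 hematological toxicity but not grade 3. Important note (1) covers grade 3, but only if judged clinically relevant. Its 50% completion test concerns administrations missed in the first four weeks, not a late cycle 2. The investigator-judged item and CMC review are open-ended, and neither requires waiting.

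**The case against.** The strongest reply is that the toxicity is the DLT and the delay only grades it. The item is worded that way, and the exception for grade 3 liver enzymes similarly looks to recovery before the next cycle is due. On that reading an onset within 28 days could count. This is a fair reading, but the protocol does not state it, and it leaves the same gap: on day 28 nobody can know whether the delay will exceed 14 days, and nothing requires anyone to wait.

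Second, the event would be visible. Blood tests are weekly in cycle 1 and repeated on day 1 of cycle 2, the CMC includes all principal investigators, and it reviews before each cohort and before the RP2D. Four weeks is also a minimum: monthly CMC meetings, screening and biopsies may use up part of the 16 days before anyone is dosed at the next level. All of this stands and narrows the gap. None of it is a rule tied to an open event.

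Three stronger readings are tempting and not supported:

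- *That the item is a dead criterion.* The 28-day limit applies to dose escalation. Dose modification, dose reduction and the phase 2 monitoring in section 7.3 state no such limit, so the item can operate there.
- *That four weeks alone clears a level for intra-patient escalation.* The CMC must also have deemed the level at or below the MTD, and the patient must have no clinically relevant drug-related toxicity above grade 1.
- *That the RP2D will be set too high.* The documents give no rate for such delays. When a level is expanded from three to six, the first three patients will usually be past day 44.

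**Conclusion.** The point holds in a limited form. Taken literally, a listed DLT criterion cannot be met before about day 44 (day 43 to 47 across the dosing window), while the escalation decision it should inform rests on 28 days. Many such events will be caught by judgment. The remainder is mainly grade 3 cytopenia that recovers slowly, has not been called a DLT by another route, and for which the CMC does not choose to wait. Its frequency cannot be derived from the documents, but with three to six patients per level a single such event changes the action.

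Phase 2 monitoring limits the harm of an RP2D set too high. Its first listed boundary is at 10 patients, however, and it cannot undo an escalation already made. The conclusion assumes nominal 28-day cycles and a decision taken at or soon after day 28 of the last starter. The later the CMC decides, the smaller the gap. This is a wording gap worth closing before escalation, not a fault in the dose-finding design.

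**What to change.** Add to Important note (1) and to the DLT definition in section 3.3.1:

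> A treatment-related toxicity with onset in the first 28 days that delays the start of cycle 2 by more than 14 days counts as a cycle 1 DLT. If a patient in the cohort has an unresolved treatment-related toxicity at day 28 of a grade that prevents the start of cycle 2 (e.g. grade 3 or higher hematologic toxicity), the CMC will not open the next level, deem the level at or below the MTD (including for intra-patient escalation), or set the RP2D until that patient starts cycle 2 or the event qualifies as a DLT.

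Tying the hold to a grade that prevents cycle 2 keeps minor unresolved toxicity from stopping escalation. Doses, cohort sizes and decision thresholds do not change. The cost is two sentences and, only for cohorts with such an event, a wait of about two weeks: 44 - 28 = 16 days on nominal days, up to 47 - 28 = 19 days with the dosing window.

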## 4. ENROLLMENT OF PATIENTS

---

Patients will be identified as potential candidates for the SPRING trial and may consent to enrollment in SPRING and to related study procedures including biopsies from the tumor tissue (metastatic lesion or primary tumor), and from its histologically matched normal tissue (bronchial mucosa).

Biopsies will be processed and investigations performed (i) to detect genomic alterations (in the case that this information is not already available from the patient's file) in order to exclude the patient from the tested tri-therapy trial if such aberrations are detected, (ii) to generate the SIMS scoring. However, the scoring will not be used other than to establish correlations retrospectively between biological data and clinical outcome. All eligible patients will receive the triple combination.

### 4.1. ELIGIBILITY CRITERIA

*Note: Eligibility criteria should be verified between consent and registration (28 days maximum window).*

**For phase 1 and phase 2:**

- Age: Men and women aged  $\geq 18$  years,
- Signed written informed consent,
- Any histologic type of locally advanced or metastatic NSCLC,
- Life expectancy of  $\geq 12$  weeks,
- Measurable or evaluable (cytologically or radiologically detectable disease such as ascites, peritoneal deposits, or lesions which do not fulfill RECIST 1.1 criteria for measurable disease) lesions according to RECIST 1.1 criteria for phase 1 portion. For phase 2, all patients must have RECIST 1.1 measurable disease,
- PHYSIOLOGIC FUNCTION:
  - ✓ Hematologic: Absolute neutrophil count (ANC)  $\geq 1.5 \times 10^9/L$ , platelet count  $\geq 100 \times 10^9/L$ , and hemoglobin  $\geq 9$  g/dL (may have been transfused),
  - ✓ Hepatic: Total bilirubin level  $\leq 1.5 \times$  the upper limit of normal (ULN) range and AST and ALT levels  $\leq 2.5 \times$  ULN,
  - ✓ Renal: Estimated creatinine clearance  $\geq 30$  mL/min according to the Cockcroft-Gault formula (or local institutional standard method).
- PREGNANCY AND CONTRACEPTION:
  - ✓ Pregnancy test: Negative serum or urine pregnancy test at screening for women of childbearing potential.
  - ✓ Contraception: Highly effective contraception for both male and female subjects throughout the study and for at least 90 days after last treatment administration if the risk of conception exists.
- Ability to comply with protocol requirements,
- Willingness to consent and ability to undergo a trucut biopsy to obtain a fresh metastasis or primary tumor biopsy, and to undergo bronchoscopy to obtain a biopsy from normal bronchial mucosa,

- No serious or medically uncontrolled concomitant conditions that are likely to make the patient unfit for SPRING combination therapy, as per investigator assessment,
- ECOG performance status of 0 to 1.

#### **4.2. EXCLUSION CRITERIA**

***Note: Exclusion criteria should be verified between consent and registration (28 days maximum window).***

- Patients with documented oncogenic aberrations at enrollment: EGFR, ALK, ROS1 when available, MET exon 14 skipping when available. For squamous undifferentiated cell carcinoma, documentation of these aberrations is not mandatory.

Note: For Phase 1 portion, all patients with adenocarcinoma histology must have documentation of results for druggable oncogenic aberrations (EGFR mutations, ALK rearrangements, and ROS1 when available) prior to enrollment on the study.

- For Phase 1 portion, >2 lines of prior therapy in the metastatic setting.
- For the dose escalation phase of the study or until the MTD for the combination regimen has been determined, patients with moderate hepatic impairment defined as AST, ALT, ALP >5 times ULN, which would be grade 3 or higher. However, patients with liver metastases with AST/ALT ≤ 5 x ULN can be included in the study.
- For Phase 2 portion, any prior therapy in the metastatic setting.

#### **Clinical criteria for phase 1 and phase 2 studies:**

- Patients with treated brain metastases are eligible as are patients with new, active untreated brain metastasis.
- Participants with a history of myocardial infarction within the last 2 years or with significant cardiac arrhythmias uncontrolled by medication or pacemaker,
- Participants with any history of interstitial lung disease,
- Prior clinically significant toxicities from anticancer agents or radiotherapy which have not regressed to Grade ≤ 1 severity (NCI-CTCAE version 4.03) apart from peripheral neuropathy and alopecia,
- History of any second malignancy in the last two years; patients with prior history of in-situ cancer or basal or squamous cell skin cancer are eligible. Patients with a history of other malignancies are eligible if they have been continuously disease-free for at least two years,
- Autoimmune condition requiring medical intervention,
- Uncontrolled concomitant illness, active infection requiring i.v. antibiotics,
- Patients who have had a thromboembolic event within six months are excluded, as are patients on anticoagulants, except for low dose aspirin (<100 mg/day) and low doses of anticoagulants meant to keep line access open;
- Patients with Grade 3 or 4 (serious) gastrointestinal bleeding within the last six months are excluded.
- Prior  $\geq$  G3 hemoptysis, major blood vessel involvement (specifically including aorta, superior and inferior vena cava, main pulmonary arteries and veins, subclavian arteries and veins and other

large blood vessels that in the investigator's opinion places the patients at high risk for major bleeding), and/or central cavitations,

- Known or suspected drug hypersensitivity to any drug used in the combination,
- Difficulty swallowing, malabsorption or other chronic gastrointestinal disease, or conditions that may hamper compliance and/or absorption of the oral drugs,
- Any condition (e.g., known or suspected poor compliance, psychological instability, geographical location, etc.) that, in the judgment of the investigator may affect the patient's ability to sign the informed consent and undergo study procedures,
- Taking another experimental drug within 28 days prior to day 1 of the protocol medications in this study,
- Pregnant or breast-feeding women,
- Both male and female patients of reproductive potential must agree to use highly effective contraception, during the study and for 3 months following the last dose of study drug,
- Patients currently taking strong CYP3A4 inducers and inhibitors, See [Appendix 9](#).
- Patients currently taking proton pump inhibitors due to their impact on the disposition of palbociclib during the phase 1.
- Patients taking other anticancer agents with the exception of denosumab or equivalent medication for bone metastases.
- A time period of at least three weeks (including radiotherapy) or five drug half-lives, whichever is shorter must have elapsed from last non-investigational therapy before first day of treatment on this study,
- A time period of at least 10 days must have elapsed from last palliative radiotherapy before the first day of treatment on this study,
- Specific exclusion criteria for administration of avelumab, in combination:
  - ✓ IMMUNOSUPPRESSANTS: Current use of immunosuppressive medication, EXCEPT for the following: a. intranasal, inhaled, topical steroids, or local steroid injection (e.g., intra-articular injection); b. Systemic corticosteroids at physiologic doses  $\leq$  10 mg/day of prednisone or equivalent; c. Steroids as premedication for hypersensitivity reactions (e.g., CT scan premedication).
  - ✓ AUTOIMMUNE DISEASE: Active autoimmune disease that might deteriorate when receiving an immuno-stimulatory agent. Patients with diabetes type I, vitiligo, psoriasis, or hypo- or hyperthyroid diseases not requiring immunosuppressive treatment are eligible.
  - ✓ ORGAN TRANSPLANTATION: Prior organ transplantation including allogenic stem-cell transplantation.
  - ✓ INFECTIONS: Active infection requiring IV (Intra venous) therapy.
  - ✓ HIV/AIDS: Known history of testing positive for HIV or known acquired immunodeficiency syndrome.
  - ✓ HEPATITIS: Hepatitis B virus (HBV) or hepatitis C virus (HCV) infection at screening (positive HBV surface antigen or HCV RNA if anti-HCV antibody screening test positive).
  - ✓ VACCINATION: Vaccination within 4 weeks of the first dose of avelumab and while on trials is prohibited except for administration of inactivated vaccines.
  - ✓ HYPERSENSITIVITY TO STUDY DRUG: Known prior severe hypersensitivity to investigational product or any component in its formulations, including known severe hypersensitivity reactions to monoclonal antibodies (NCI CTCAE v4.03 Grade  $\geq$  3).

- ✓ CARDIOVASCULAR DISEASE: Clinically significant (i.e., active) cardiovascular disease: cerebral vascular accident/stroke (< 6 months prior to enrollment), myocardial infarction (< 6 months prior to enrollment), unstable angina, congestive heart failure ( $\geq$  New York Heart Association Classification Class II), or serious cardiac arrhythmia inadequately controlled by medication.
- ✓ OTHER PERSISTING TOXICITIES: Persisting toxicity related to prior therapy (NCI CTCAE v. 4.03 Grade  $> 1$ ); however, alopecia, sensory neuropathy Grade  $\leq 2$ , or other Grade  $\leq 2$  not constituting a safety risk based on investigator's judgment are acceptable.
- ✓ Other severe acute or chronic medical conditions including colitis, inflammatory bowel disease, pneumonitis, pulmonary fibrosis or psychiatric conditions including recent (within the past year) or active suicidal ideation or behavior; or laboratory abnormalities that may increase the risk associated with study participation or study treatment administration or may interfere with the interpretation of study results and, in the judgment of the investigator, would make the patient inappropriate for entry into this study.

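### Section 4.2 both excludes and admits some patients with treated autoimmune disease, and its infection and arrhythmia exclusions are looser than the avelumab minimum stated in Appendix 6 Table 1

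*Combined protocol and SAP*

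**What the plan says.** Section 4.2 has two lists that apply to both phases.

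- **General clinical criteria.** One line excludes "Autoimmune condition requiring medical intervention". It does not define medical intervention, states no exception and does not refer to the later list. The same list excludes "active infection requiring i.v. antibiotics" and significant arrhythmia that neither medication nor a pacemaker controls.
- **Avelumab-specific criteria.** The autoimmune item excludes "Active autoimmune disease that might deteriorate when receiving an immuno-stimulatory agent" and continues: "Patients with diabetes type I, vitiligo, psoriasis, or hypo- or hyperthyroid diseases not requiring immunosuppressive treatment are eligible". The immunosuppressant item excludes current use but permits "intranasal, inhaled, topical steroids, or local steroid injection" and "Systemic corticosteroids at physiologic doses" (up to 10 mg/day of prednisone or equivalent). The infection item is limited to intravenous therapy. The arrhythmia item is limited to serious arrhythmia that medication does not adequately control.

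Appendix 6, section 1, describes its Table 1 as the minimum required safety-related criteria for avelumab. It then provides for further criteria on top of them. Table 1 repeats the autoimmune wording, but on two items it goes further than section 4.2: it excludes active infection needing systemic therapy by any route, and serious arrhythmia for which medication is needed.

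**The concern.** There are two separate problems.

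The first lies inside section 4.2. The general line tests whether the condition needs medical intervention. The avelumab line tests whether it needs immunosuppression. Some named conditions are treated without immunosuppression, so the two tests can give opposite answers, and two sites could decide differently on the same patient. Eight centres are planned (2 + 5 + 1, section 1.1).

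The second is a mismatch between section 4.2 and Appendix 6. Sites reading section 4.2 will agree with each other on infection and arrhythmia, but the rule they share is looser than the one the protocol calls the avelumab minimum.

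Both affect who enters a trial whose first primary objective is the safety of the combination (section 3.1). Appendix 8 lists infection at more than 10% for palbociclib, sepsis at 1% to 10% for avelumab, and cardiac arrest as a serious event common to all three drugs. Phase 1 cohorts start at three patients, and one dose-limiting toxicity triggers three more at that level (section 3.3.1), so the make-up of a cohort matters.

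**Working it through.** No arithmetic applies. The check takes each patient type through each list, looking only at the line concerned.

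| Patient | 4.2 general list | 4.2 avelumab list | Appendix 6 Table 1 |
|---|---|---|---|
| Type 1 diabetes on insulin | Excluded | Eligible | Eligible |
| Autoimmune thyroid disease on hormone replacement | Excluded | Eligible | Eligible |
| Psoriasis on topical steroid | Excluded, if topical treatment counts as medical intervention | Arguable | Arguable |
| Untreated vitiligo or psoriasis | Not excluded | Eligible | Eligible |
| Thyroid disease that is not autoimmune, no immunosuppression | Not reached | Eligible | Eligible |
| Active infection on oral systemic treatment | Not excluded | Not excluded | Excluded |
| Serious arrhythmia adequately controlled by medication | Not excluded | Not excluded | Excluded |

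**Autoimmune rows.** The first two are clear conflicts. The protocol itself names insulin for type 1 diabetes and thyroid hormone for hypothyroidism in Appendix 6 Table 4. That table concerns reactions arising on treatment, but it shows that the protocol regards both as treatment, and neither is immunosuppression. The psoriasis row is doubtful: section 4.2 lists topical steroids as a permitted form of immunosuppressive medication, so such a patient may not count as free of immunosuppressive treatment. Untreated disease, and thyroid disease that is not autoimmune, raise no conflict.

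**Infection and arrhythmia rows.** Neither list in section 4.2 restores the Table 1 rule. Appendix 6, section 1, provides for adding criteria to the minimum and says nothing about relaxing it.

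**Comparison with myocardial infarction.** The general list excludes a "history of myocardial infarction within the last 2 years", while the avelumab list excludes "myocardial infarction (< 6 months prior to enrollment". Both lines only exclude, so the longer window governs and there is no contradiction. The autoimmune pair differs because one of its lines affirmatively declares patients eligible.

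**Why the general autoimmune line should stay.** Quiescent autoimmune disease on prednisone up to 10 mg/day can pass both the immunosuppressant and the autoimmune items of the avelumab list. The general line is what excludes it.

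**The case against.** On the autoimmune point, the best defence is that exclusion criteria are cumulative. A patient must clear every line, and the eligibility sentence may limit only the avelumab item in which it sits. The general line would then be an additional trial-level criterion of the kind Appendix 6 allows. This reading is possible, and the sentence would keep some effect for untreated disease and for thyroid disease that is not autoimmune. For type 1 diabetes, however, it leaves the statement with almost no effect. The protocol does not say which reading applies. Elsewhere in the general list, exceptions are written into the bullet itself (prior malignancy, anticoagulants, residual toxicity); the autoimmune bullet has none.

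On infection and arrhythmia, a reader might infer that sites will enrol patients below the avelumab minimum. The documents support only that they may. The eligibility criteria require the absence of serious or uncontrolled conditions that make the patient unfit, and section 4.2 excludes uncontrolled concomitant illness and conditions the investigator judges unsuitable. These clauses can stop some such patients, but they are discretionary and do not reproduce a fixed rule. It can also be argued that a fully controlled arrhythmia is not active cardiovascular disease, the umbrella term in Table 1; even so, the Table 1 arrhythmia item turns on the need for medication.

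Table 1 may be generic avelumab text that section 4.2 adapted on purpose. Contraception also differs: 90 days in section 4.1 against 60 in Table 1. That change is stricter, though, and the documents do not show whether the looser items were deliberate.

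It is also true that a single-arm trial has no arms to unbalance and that no endpoint definition changes. This limits the consequence but does not remove the inconsistency.

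**Conclusion.** Both points hold and should be corrected.

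1. Section 4.2 gives opposite answers for insulin-treated type 1 diabetes and for autoimmune thyroid disease on hormone replacement. This assumes that medical intervention, which the protocol leaves undefined, includes insulin and hormone replacement. Topically treated psoriasis is arguable. A wider claim that every listed condition, or all thyroid disease, is in conflict is not supported.
2. Section 4.2 is looser than the stated avelumab minimum for two patient types: active infection on oral systemic treatment, and serious arrhythmia controlled by medication. Sites following it may admit such patients, subject to investigator judgement. Which text was intended cannot be told from the documents.

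The documents give no prevalence for any of these patients, so the number affected is unknown; it is probably small. No power, alpha or sample size figure changes. What matters is a consistent safety population, and a protocol that does not fall below its own stated minimum.

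**What to change.** **Autoimmune line.** Keep "Autoimmune condition requiring medical intervention" in the general list and add: *except the conditions named as eligible under the avelumab-specific autoimmune criterion (not requiring immunosuppressive treatment; insulin or thyroid hormone replacement does not exclude)*. The sponsor should confirm whether antithyroid or topical treatment is also allowed, since the documents do not settle it. The cost is that some treated patients with the named conditions, whom some sites might now exclude, would enter. Other treated autoimmune disease stays excluded.

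**Infection and arrhythmia.** Align section 4.2 with Table 1: exclude active infection needing systemic therapy (both lists) and serious arrhythmia needing medication (avelumab list), and keep the general exclusion for uncontrolled arrhythmia. The cost is screening out a few patients on oral anti-infectives or with drug-controlled serious arrhythmia. Only if the relaxation was deliberate and agreed, amend Table 1 and Appendix 6, section 1, instead, so that they no longer state a stricter minimum. That screens out no one but lowers the stated avelumab minimum.

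Both changes are to wording only.
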